Power. The sample size for the Aim 1 feasibility study is based on our original SHE study pilot and expanded to allow for rigorous testing and refining of modality.²⁶ The sample size of N~200 for the Aim 2 RCT was determined to provide satisfactory power ($\geq 80\%$) for this study in addressing the specific aims, which depends on the following parameters: number of participants (n), number of measurements (t=3 for health literacy for screening; t=4 for screening/risk reduction practices), effect size (f) as group difference in change, correlation between repeated measures (r), and attrition rate. The effect sizes estimated from the original SHE study were in the small to moderate range—for health literacy (8 domains), average $f=0.13$ at immediately post-intervention and 0.16 at 1-year post-intervention; $f=0.17$ for cervix screening and 0.12 for condom use during the last intercourse at 1-year post-intervention. Although effect sizes for breast cancer screening and STI screening are not available from the original SHE study, we expect similar, small to moderate effect sizes for these outcomes. Thus, we conservatively assumed the smallest observed effect size of $f=0.12$ for our power calculation. The correlations between repeated measures observed in the original SHE study were $r=0.46$ on average, with the range of 0.39-0.75 between baseline and immediately post-intervention and 0.25-0.61 between baseline and 1-year post-intervention. Power analysis of these data ($f=0.13$, $t=3$ or 4, $r=0.46$) and G*Power 3.1.9.2 indicated that a sample of 124 women will produce $\geq 80\%$ power for both health literacy (80%) and screening/risk reduction behaviors (85%). In our original SHE study, the 3-year follow-up rate was 85%. Conservatively assuming a high attrition rate up to 40%, we will recruit ~200 women at baseline to adequately power the SHE-Women study—i.e., maintain $\geq 80\%$ power even with a low follow-up rate as small as 60%. As

Table 4. Expected attrition over study period

	Aim 1 feasibility Target N~20	Aim 2 RCT Target N~200	Aim 3 (same as Aim 2)
Consent and baseline	20	260	--
Intervention initiation	15	220	--
Post-intervention	10	200	--
1 year follow-up	--	170	--
2-year follow-up	--	160	--
3-year follow-up	--	150	--

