described above, missing data due to either attrition or nonresponse will be fully recovered via multiple imputation in our intent-to-treat analysis, which will provide additional power and remove any confounding effect of missing data on our statistical power. For Aim 3, the key stakeholder interviews will occur with enough research participants to reach thematic saturation. Based on prior experience with key stakeholder interviews, we believe N~20 interviews will accomplish this goal,²⁷ but have resources to interview additional participants. Additionally, our COVID-19 module interview suggests N~30 interviews will accomplish the goal of thematic saturation.

Outcomes and instruments. Aim 1 feasibility outcomes include uptake of intervention components, barriers and facilitators of implementation, problems with delivery, and necessary modifications.⁴⁵ Pilot effectiveness outcomes will include an assessment of women's health literacy, operationalized as knowledge, beliefs, and self-efficacy for screening related to cervical, breast cancer, birth control, and STIs, post-intervention.^{4,26} Aim 2 RCT outcomes include women's health literacy, immediately post-intervention and 1-year post-intervention; and screening/ risk reduction for cervical, breast cancer, unintended pregnancy, and STIs at 1, 2, and 3-years post-intervention. Aim 3 outcomes include perception and uptake of intervention components.⁴⁵

Feasibility and perception of intervention outcomes are defined below and assessed through participant tracking and key stakeholder interviews with a subset of participants.:

- *Uptake of integrated, multimedia electronic women's health literacy intervention:* documentation of number of participants who responded to text messages; clicks on Website; real-time assessment of knowledge; time elapsed between text messages and Website clicks; number of outreach messages (through text, phone, or Facebook); Facebook posts/messages; chats with health educator; total minutes of contact through text, Web, chat, Facebook with each participant; attendance at community sessions
- *Barriers and facilitators of implementation:* problems described by participants in setting up text message platform, Website, closed Facebook group; factors that make set up of text message platform, Website, closed Facebook group ease of use; ease of Website components use (content modules, assessments)

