Using quantitative data from the pilot trial of the SHE-Women text-Web intervention, we will conduct descriptive analysis and bivariate tests to explore women's health literacy (knowledge, beliefs, and self-efficacy) for screening related to cervical, breast cancer, birth control, and STIs (Aim 1). The results including effect sizes estimated for the outcome will be utilized for refinement of the intervention content and modality. To test the hypothesis that SHE-Women will be more effective than standard of care at improving outcomes (Aim 2), we will utilize mixed modeling techniques for repeated measures, separately for each outcome variable: health literacy for screening and screening/risk reduction practices. General/generalized models will evaluate the effects of the intervention by estimating overall group difference across measurements (i.e., group effect), change over time (i.e., time effect), and group difference in change (i.e., group-by-time interaction). In other words, we will evaluate whether the intervention vs. control group improves in outcomes over time. The models will account for the impacts of sociodemographic characteristics as well as other cross-cutting risk factors including tobacco use, alcohol use, criminal justice involvement, intimate partner violence, lack of continuous health care coverage or primary care contact, etc. (covariates), thereby providing unbiased estimates of the intervention effects. The models for screening/risk reduction behaviors will also consider knowledge about cervix cancer, breast cancer, birth control, or STI as an additional covariate for the respective outcome variable. Incorporating participant tracking data, descriptive analysis and bivariate tests will demonstrate the pattern and uptake of various intervention components as measured by number of participants who responded to text messages; clicks on the Website; interactive clicks on the Website, e.g. through real-time assessment of knowledge; time elapsed between text messages and Website clicks; number of outreach messages (through text, phone, or Facebook); Facebook posts/messages; chats with health educator; total minutes of contact through text, Web, chat, Facebook with each participant; and attendance at community sessions (Aim 3). General/generalized mixed modeling for repeated measures will assess the impacts of the uptake on each outcome variable of health literacy for screening and screening/risk reduction practices while controlling for the impact of sociodemographic characteristics and other risk factors. A proper covariance structure for repeated measures will be chosen for each outcome variable based on model fit (i.e., likelihood, Akaike Information Criterion, adjusted Bayesian Information Criterion). Statistical significance will be determined at 0.05 alpha level, and all analyses conducted using SAS 9.4⁵⁹

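### The 80% and 85% power figures hold at one average correlation (r=0.46); lower down the plan's own 0.25-0.61 range, 124 completers give less than 80%, and the plan does not say so

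*Combined protocol and SAP*

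**What the plan says.** The Power paragraph (under APPROACH) defines the effect as the group difference in change and gives the "number of measurements (t=3 for health literacy for screening; t=4 for screening/risk reduction practices". It reports correlations from the original SHE study: 0.46 on average, with 0.39-0.75 "between baseline and immediately post-intervention and 0.25-0.61 between baseline and 1-year post-intervention". Nothing is given for years 2 and 3, and no outcome is attached to either end of a range.

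On effect size it says: "Thus, we conservatively assumed the smallest observed effect size of $f=0.12$ for our power calculation". Shortly afterwards it prints a different value: "Power analysis of these data ($f=0.13$, $t=3$ or 4, $r=0.46$) and G*Power 3.1.9.2 indicated" that 124 women give 80% power for health literacy and 85% for screening/risk reduction. It then says that recruiting about 200 keeps power at 80% or more "even with a low follow-up rate as small as 60" per cent.

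The Outcomes and instruments paragraph places "screening/ risk reduction for cervical, breast cancer, unintended pregnancy, and STIs at 1, 2, and 3-years post-intervention", so this family has no immediate post-intervention visit. The Data analysis paragraph fits repeated-measures mixed models "separately for each outcome variable: health literacy for screening and screening/risk reduction practices", and adds: "Statistical significance will be determined at 0.05 alpha level".

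**The concern.** In a test of group-by-time interaction, the correlation between repeated measures sets the error variance of change through the factor (1-r). Each outcome has its own model, so its power depends on its own correlation, and an average does not protect the outcomes below it. Moving from r=0.46 to r=0.25 multiplies the noncentrality by 0.54/0.75 = 0.72, a loss of 28%.

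The plan is cautious on effect size (the smallest f observed) and on attrition (up to 40%), but takes the mean for the correlation. It then states the result without condition for both outcome families. For screening/risk reduction, the 0.39-0.75 range describes a visit that family does not have.

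At stake is how a null result is read. If an outcome with a low correlation ends with about 124 completers, readers will believe the chance of missing the planned effect was at most one in five, when it could be nearer one in three (three measurements) or one in four (four).

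**Working it through.** **Inputs.** From the Power paragraph: N=124; f=0.12 (assumed) or 0.13 (printed); t=3 or 4; r=0.46 on average; baseline-to-1-year range 0.25-0.61. Two arms and alpha 0.05. From Table 4: 170 women at 1 year and 150 at 3 years.

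**Method.** The plan names G*Power but not the procedure. I used its repeated-measures within-between interaction, with sphericity and one common correlation for all visit pairs:

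- noncentrality = N × t × f² / (1-r)
- degrees of freedom = (t-1) and (N-2)(t-1)
- power from the noncentral F distribution.

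**Step 1: reproduce the plan (r=0.46, N=124).**

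- f=0.12, t=3: 124 × 3 × 0.0144 / 0.54 = 9.92; df 2 and 244; power 80.7% (stated 80%).
- f=0.12, t=4: 124 × 4 × 0.0144 / 0.54 = 13.23; df 3 and 366; power 87.3% (stated 85%).
- The MANOVA form of the same test gives 80.2% and 86.5%.
- The printed f=0.13 gives 86.9% and 92.4%. It approaches the stated figures only with an unstated sphericity correction of about 0.75 (78.9% and 85.7%).

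So f=0.12 is the better reading, and the stated figures are about right at the average correlation.

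**Step 2: vary r (N=124, f=0.12).**

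| r, all visit pairs | t=3 | t=4 |
|---|---|---|
| 0.25 | 65.9% | 73.3% |
| 0.43 (midpoint of 0.25-0.61) | 78.4% | 85.3% |
| 0.46 | 80.7% | 87.3% |
| 0.61 | 92.0% | 96.0% |

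Power reaches 80% at r of about 0.45 for t=3. For t=4 it is 79.9% at r=0.35 and 80.6% at r=0.36. With f=0.13 and r=0.25, power is 73.3% and 80.6%.

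**Step 3: unequal correlations for literacy.** A literacy domain at the bottom of both ranges has 0.39 (baseline to post) and 0.25 (baseline to 1 year). The post-to-1-year value is not given; I assumed 0.25 to 0.60. A sustained effect of the size that f=0.12 implies then has 65-72% power. Averaging the three correlations instead, with the third assumed to be 0.25-0.46, gives about 69-74%. If that domain's baseline-to-post value were 0.75, the averaging method would give about 77-83%.

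**Step 4: expected retention (f=0.12, r=0.25).**

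- 170 completers, t=3: 170 × 3 × 0.0144 / 0.75 = 9.79; power 80.3%.
- 150 completers, t=4: 150 × 4 × 0.0144 / 0.75 = 11.52; power 82.0%.

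**Step 5: 60% follow-up with partial data kept (f=0.12, r=0.25, 200 women at baseline, likelihood-based mixed model).** For an effect sustained from the first follow-up:

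- t=3, 200 at post and 120 at 1 year: 83%.
- t=3, all loss before post (120 and 120): 75%.
- t=4, 120 at each follow-up: 83%.
- t=4, 160, 140 and 120: 87%.

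For an effect present only at the last visit, power is about 68% (t=3, loss after post) and 73-74% (t=4).

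**The case against.** The strongest reply is that the plan does not analyse completers only. It fits mixed models and adds multiple imputation, so women with partial data contribute. Step 5 shows that at 60% follow-up and r=0.25, several loss patterns still exceed 80% for a sustained effect. This stands. A reader might infer that the 60% follow-up claim is false and should be deleted; the documents do not support that. The claim is conditional on the correlation and on when effects and losses occur, and the plan does not state those conditions.

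A reader might also infer an arithmetic error. There is none on this point: 80% and 85% are close to what the average correlation gives, and both ranges are disclosed. Planning on an average is common practice.

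The 66% and 73% stack worst cases, which also stands. The value 0.25 is the minimum for one visit pair of an outcome that is not named, so the documents do not show it in both families. The plan does not say that 0.25-0.61 covers screening items, and f=0.12 is the condom-use value. Average literacy effects were 0.13 and 0.16, and cervix screening 0.17. At r=0.25 with 124 women, f=0.16 (t=3) gives 90% and f=0.17 (t=4) gives 97%.

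Finally, some screening outcomes apply only to subgroups. Mammography is for age 50 and over, who were 23 of 261 women in Table 1. No power figure at 124 women describes that outcome.

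What survives is narrower. The plan itself assumed f=0.12 for every outcome and stated 80% or more without condition, and that statement fails inside its own reported range.

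**Conclusion.** The power statement is right at the average correlation but omits its dependence on r, and for literacy it has almost no margin: 80.7% at r=0.46, with the 80% line at about 0.45. For four measurements there is more room, down to about 0.36. At the low end of the reported range, 124 completers give about 66% and 73% (f=0.12), or 73% and 81% (f=0.13). These are worst-case figures, assuming one correlation for all visit pairs, sphericity and complete data.

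At central values the target is broadly met. The average of 0.46 meets it for both families. The midpoint of 0.43 gives 85.3% for t=4 and 78.4% for t=3; the latter is pessimistic because literacy also has the more highly correlated baseline-to-post pair. The retention expected in Table 4 meets the target even at r=0.25.

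A reader might infer that the trial is underpowered or needs more women. That does not follow; the defect is in what the plan promises at low follow-up.

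**What to change.** In the Power paragraph:

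1. Restate 80% and 85% as power at the average correlation of 0.46.
2. Add the range over the plan's own correlations: with f=0.12 and 124 completers, about 66-92% for three measurements and 73-96% for four, for r from 0.25 to 0.61. Label it as assuming that this range applies to each outcome family and to all visit pairs, and say that it does not describe outcomes defined only in a subgroup, such as mammography.
3. Limit the 60% follow-up claim, on a completers basis, to outcomes with r of about 0.45 or more (three measurements) or 0.36 or more (four). Note that women with partial data in the mixed model can raise power, depending on when the effect and the losses occur.
4. Reconcile the assumed f=0.12 with the printed f=0.13, and name the G*Power procedure and any sphericity correction.

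This takes a few sentences. Sample size, design and conduct are unchanged; the only downside is a less favourable stated figure.

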
Table 1. Justice-involved women's health risk, N=261	N (% or SD)
Cervical cancer risk	
No Pap test in past 3 years	59 (22.6)
Lifetime abnormal Pap test	126 (48.2)
Cervical cancer diagnosis	30 (11.4)
Breast cancer risk	
No mammogram for 50 or older (N=23) in past 2 years	11 (47.8)
Unintended pregnancy risk	
Lifetime unintended pregnancy	207 (79.3)
No past month birth control use (excluding hysterectomy)	76 (29.1)
Sexually transmitted infection risk	
Lifetime STI history	163 (62.4)
No condom use at last sex	196 (75.1)
Ever sold sex	91 (34.8)
Cross-cutting risk factors	
Past month tobacco use	205 (78.5)
Alcohol use problem	132 (50.5)
Past year drug dependence	163 (62.4)
Lifetime mental health diagnosis	191 (73.1)
Past year intimate partner violence	133 (50.9)
Uninsured	160 (61.3)
No primary care doctor	150 (57.4)
No medical home	70 (26.8)
Lifetime months incarcerated, Mean	24.2 (45.3)
Race/ethnic group with higher cancer mortality	
e.g. Black	83 (31.8)
e.g. Hispanic	21 (8.0)
Age, Mean	33.7 (±9.9)

Table 2. SHE-Women - A women's health literacy curriculum

Knowledge of cervical, breast cancer, birth control, and STIs	Beliefs about cervical, breast cancer, birth control, and STIs	Self-Efficacy for cervical, breast cancer, birth control, and STI screening	Confidence navigating health systems for screening and risk reduction
Female body anatomy Medical terminology How stuff works in the body, prevention, and cures Procedures Costs	Beliefs about disease Beliefs about screening Where you learned about sex/health/prevention? What do you share with kids, partners? Romantic/sexual relationship dynamics Experiences with providers Motivations for screening and prevention	What is self-efficacy? Do you know where to go for services/experiences at these places/barriers? Do romantic/sexual partners get in the way/help? How to get results? What makes it easy to get services? Drug use/ homelessness/ transportation/ financial/ other barriers – how to overcome?	Confidence navigating providers given long-term criminal justice involvement? Jail health care and services, trust, cost Outside of jail services, trust, cost, fears Insurance/no insurance Social support for health care seeking Coercion

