- *Potential problems with delivery of intervention:* number of incorrect phone numbers, changed phone numbers; problems with Website described by participants and staff; description of level of annoyance with outreach messages through text, phone, and Facebook; number of participants re-incarcerated during intervention trial and, thus, resulted in non-completion; problems with chat feature with health educator
- *Modifications needed to maximize implementation:* suggestions from participants about improving multimedia electronic approaches; suggestions about improving real-time assessments of knowledge
- *Perception of human interaction in intervention:* positive and negative aspects of multimedia electronic educational interventions; benefits and disadvantages to offer of community-based sessions; perceived value of human face in video/audio intervention content; advantages/disadvantages of conversation during discharge planning session for control arm

Women's health literacy and screening/risk reduction outcomes are described in Table 5 below. Items will be adapted from scales listed in Table 5.

Table 5. Women's health literacy and screening/risk reduction outcomes and instruments	
Women's health literacy (Knowledge, beliefs, self-efficacy, confidence navigating systems)	Screening/ Risk reduction
Cervix literacy Pap knowledge scale ⁴⁶ Health belief model scale for cervical cancer and Pap smear test ⁴⁷ Self-efficacy for cancer screening scale ⁴⁸ Confidence navigating health systems scale (cervix, breast, birth control, STI) ⁴	Up-to-date Pap exam or HPV co-testing Abnormal Pap follow-up HINTS cervical cancer screening questions ⁴⁹ Original SHE HPV co-testing and abnormal Pap follow-up questions ⁴
Breast literacy Knowledge, beliefs, self-efficacy items from breast cancer literacy assessment ⁵⁰	Up-to-date screening mammography (biennial) for age 50+ HINTS breast cancer screening questions ⁴⁹
Birth control literacy Contraceptive knowledge assessment ⁵¹ Beliefs about acquisition and use of contraceptive items from self-efficacy scale ⁵²	Current use of hormonal or long-acting reversible birth control method, if no menopause or sterilization BRFSS birth control questions ⁵³
Sexually transmitted infection literacy STD knowledge questionnaire ⁵⁴ Multidimensional condom attitudes scale ⁵⁵ Condom self-efficacy scale ⁵⁶	Condom use at last sex STI treatment BRFSS condom use and STI treatment questions ⁵³

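### The 85% power for screening/risk reduction matches a continuous-score calculation, was not worked out for the planned yes/no models, and sits beside two conflicting effect sizes

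*Combined protocol and SAP*

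**What the plan says.** The Power paragraph (under Approach) defines f as the between-group difference in change. It takes three measurements for health literacy and four for screening/risk reduction. On effect size it says: "Thus, we conservatively assumed the smallest observed effect size of $f=0.12$ for our power calculation". The result follows with a different value: "Power analysis of these data ($f=0.13$, $t=3$ or 4, $r=0.46$) and G*Power 3.1.9.2 indicated". The same sentence gives the sample size, "and G*Power 3.1.9.2 indicated that a sample of 124 women will produce" at least 80% power, namely 80% for health literacy and 85% for screening/risk reduction. About 200 women are recruited so that power stays at 80% or more even with 60% follow-up.

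Table 5 lists the screening/risk-reduction outcomes. They are mainly statuses: up-to-date Pap or co-test, up-to-date mammography, current use of a contraceptive method, and "Condom use at last sex". The Data analysis section names the model family: "General/generalized models will evaluate the effects of the intervention by estimating overall group difference across measurements", together with change over time and the group-by-time interaction. It adds: "Statistical significance will be determined at 0.05 alpha level". No event rate, risk difference or odds ratio is assumed for the RCT.

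**The concern.** A power figure is informative only for the test that will be run. An f, a number of visits and a single correlation describe a continuous response with constant variance. For a yes/no outcome the variance depends on the proportion, the planned test works on the logit scale, and the effect is bounded by 0% and 100%. The section never turns f into percentages, so a reader cannot see how large a difference is being assumed.

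Screening/risk reduction is one of the two Aim 2 effectiveness outcomes, and the Validation strategies section counts it among the primary outcomes. If the 85% stands, a null result could be taken as an adequately powered negative when only large differences were detectable.

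**Working it through.** **1. Reproduce the plan's figures.** Inputs from the Power section: N=124, r=0.46, t=3 or 4, f=0.12 or 0.13, alpha 0.05, two groups. For the repeated-measures within-between interaction, lambda = N·t·f²/(1−r), with df = (t−1) and (N−2)(t−1).

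| f | t | lambda | power | stated |
|---|---|---|---|---|
| 0.12 | 3 | 124·3·0.0144/0.54 = 9.92 | 80.7% | 80% |
| 0.12 | 4 | 124·4·0.0144/0.54 = 13.23 | 87.3% | 85% |
| 0.13 | 3 | 124·3·0.0169/0.54 = 11.64 | 86.9% | 80% |
| 0.13 | 4 | 124·4·0.0169/0.54 = 15.52 | 92.4% | 85% |

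At f=0.12 the formula gives the 80% and comes within 2.3 points of the 85%. At the printed f=0.13 it gives neither.

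**2. Turn f into percentages.** Assume no difference at baseline and a constant difference delta (in SD units) at years 1, 2 and 3. The interaction effect is f = (delta/2)·√(3/16) = 0.2165·delta, so f=0.12 means delta = 0.12/0.2165 = 0.554 SD.

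- Condom use: Table 1 gives 75.1% for "No condom use at last sex", so use is 24.9%. SD = √(0.249·0.751) = 0.432, and 0.554·0.432 = 24.0 points (24.9% to 48.9%).
- Pap: Table 1 gives 22.6% for "No Pap test in past 3 years", so about 77.4% are up to date. SD = √(0.774·0.226) = 0.418, and 0.554·0.418 = 23.2 points. Only 22.6 points are available if controls stay flat (77.4 + 23.2 = 100.6%).
- Log-odds scale: log OR = 0.554·π/√3 = 1.005. This takes condom use to 47.5% and Pap to 90.3%.

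**3. Power under logistic models.** Simulated trials had 62 women per arm, four correlated yes/no measurements (r=0.46), a flat control arm and a 3-df group-by-visit test (2,000 trials per scenario). Results for condom use:

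| f and scaling | intervention rate | marginal logit, robust Wald | random-intercept logistic, Wald | random-intercept logistic, LR |
|---|---|---|---|---|
| 0.12, log odds | 47.5% | 68.8% | 69.0% | 71.2% |
| 0.12, baseline SD | 48.9% | 72.2% | 72.4% | 75.2% |
| 0.12, average cell SD | 50.3% | 78.7% | 79.5% | 81.7% |
| 0.13, log odds | 49.6% | 74.6% | 75.1% | 77.1% |
| 0.13, baseline SD | 50.9% | 78.7% | 79.7% | 81.8% |
| 0.13, average cell SD | 52.4% | 85.2% | 86.4% | 87.5% |

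Null rejection was 4.8-6.0%. A separate simulation of the f=0.12 baseline-SD case gave 68.8% (marginal Wald) and 74.3% (random-intercept LR). A linear test of the same yes/no data gave 83-84%, so most of the loss comes from the logit scale.

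**4. Other cases.**
- 150 women (Table 4, year 3), f=0.12, baseline SD: 77-84% for condom use.
- Pap on the log-odds scale, 124 women: 49-59% at f=0.12 (target 90.3%) and 57-66% at f=0.13 (target 91.1%).
- A sustained 10-point difference, 124 women: about 18% for condom use and 26-30% for Pap.

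**The case against.** The case for the plan has four parts, and much of it stands.

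- **The ANOVA origin is inferred.** The G*Power routine is not named, and the formula gives 87.3% or 92.4% for four visits, not 85%. A reader might state the ANOVA as fact, but the documents support it only as the natural reading of the inputs.
- **A single low figure for condom use would be too strong.** A reader might infer that power is simply 69-74%. That depends on f=0.12, on the scaling and on a flat control arm. At f=0.13 with average-cell-SD scaling, power is 85-88%. If the arms move in opposite directions (12.9% against 36.9%, r=0.40), f=0.12 also gives 85-88%. The plan states none of these scenarios, so none can be credited to it or held against it.
- **The Pap effect is not shown to be unattainable.** A reader might infer this from the 100.6%. The margin is 0.6 points on the risk-difference scale, and a control decline of under one point removes it. If control falls to 65.8% and intervention rises to 89.0%, power is about 87-89%. The plan also reports f=0.17 for cervix screening at 1 year in the parent study. On a two-visit version of the same conversion with flat controls, the ceiling is (0.226/0.418)/4 = 0.135, so the sponsor's f may not map to percentages in this way. Table 1's three-year Pap item is also not identical to the Table 5 outcome.
- **124 is close to the worst case.** It is 62% of 200, while Table 4 expects 150-170 at follow-up. At 150 women most of the condom-use results reach 80%. But the 85% is quoted at 124 women and the assurance is given for 60% follow-up, so 124 is the number at which to test them.

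The simulations also leave out the planned covariates, the covariance selection and the multiple imputation. They show how sensitive power is to the model, and are not a final figure.

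**Conclusion.** The point holds in a limited form. The 85% is not shown for the planned analysis of the yes/no outcomes: no binary-model power is given, the inputs fit a continuous-score test, and the f printed beside the result does not reproduce it.

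At 124 women, condom-use power is about 69-82% for f=0.12 on all three scalings and for f=0.13 on two of them; only f=0.13 with average-cell-SD scaling reaches 85% with a flat control arm. For Pap, the f=0.12 effect slightly exceeds the room available on the risk-difference scale with flat controls. On the odds-ratio scale it is attainable but has about 49-59% power.

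These figures assume that the RCT women resemble Table 1, the control arm is flat, the effect is equal at all three follow-ups, allocation is 1:1, and r=0.46 applies to binary items. A reader might conclude that the trial is too small. The documents do not support that, because the power depends on proportions that the plan never states.

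**What to change.** In the Power section:

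1. Reconcile f=0.12 with f=0.13, and name the G*Power routine.
2. Keep the ANOVA calculation for the continuous health literacy scores only.
3. For screening/risk reduction, replace the 85%, and the assurance of at least 80% at 60% follow-up, with power from the generalized mixed model in the Data analysis section. Give it at 124 and 150 women for the group-by-visit test.
4. For each yes/no outcome, state the assumed control proportion over time and the difference in percentage points. Report power as a range with its assumptions, and include a modest difference such as 10 points.

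The cost is a short simulation, one rewritten paragraph and a less favourable stated power. Sample size, recruitment and data collection do not change.
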